7.2 Potential Benefits

This is not a treatment study. Participants can decide not to participate in the study. Participants do receive copies of laboratory tests within 1-3 weeks after their study visit. These results do not replace tests completed by their primary care physicians. Copies of these tests will only be provided to their physicians after proper written release has been obtained.

Results that require immediate follow-up are communicated to the participant within 1 business day after the results become available to the staff, in person or by telephone. Information is provided to the participant's physician if the participant consented to the release of information to the physician (completed the *Medical Release* form). We do not provide treatment for these conditions at NIH. The long-term benefit is that data and information gathered from this pilot will be used to design a treatment study in people with mild cognitive impairment/AD.

8 Research Use of Stored Human Samples, Specimens or Data

Intended Use: Specimens of blood, cells and other biological material are stored in a “biological bank” and used for this study only. Strict privacy about the samples is maintained.

8.1 Storage

Samples are kept at between -80 and -150°C. Barcoded labels will contain the following information: the participant ID, the date and visit number of the sample collected and the specimen type. No other information is reported on the label. Samples are kept indefinitely, controlled and managed by the Principal Investigator (PI) and the NIA. The origin of the samples is kept private to the extent possible by the law. Use of the biological samples is limited to designated investigators under the auspices of the NIA Scientific Director and the authorization and supervision of the Principal Investigator. Official NIA collaborators may receive samples as part of a collaborative project with NIH.

8.2 Tracking

Tracking of samples is done through an electronic database that creates a correspondence between the information contained in the specimen label and its position in the specific freezer of the biological bank. All freezers are maintained by the NIA. Specimens are managed only by NIA authorized employees. Random quality control checks are conducted regularly.

8.3 Data

The NIA ISSO approved secure web-based study repository system will present electronic source documents and Case Report Forms (CRFs) for collecting and storing study data. The web-based study repository is password protected and maintained on the secure NIA/NIH Intranet with access limited to authorized NIA personnel only. Research use of stored study data can only be granted by the Study PI. with the appropriate documentation and approvals.

8.4 Disposition at the Completion of the Protocol

All samples in this pilot study will be stored in the NIA biological bank and will be maintained indefinitely.

8.5 Reporting the Loss or Destruction of Samples/Specimens/Data to the IRB

Regardless of the reason or circumstances, loss of any biological samples will be reported to the IRB.

- Any loss or unanticipated destruction of samples or data (for example, due to freezer malfunction) that compromises the scientific integrity of the data collected for the study; will be reported to the NIDDK IRB.
- Additionally, participants may decide at any point not to have their samples stored. In this case, the principal investigator will destroy all know remaining samples and report what was done to both the subject and the IRB. This decision will not affect the subject's participation in any other protocol at NIH.

9 Assessment of Safety

9.1 Event Characterization and Reporting to the IRB and the Clinical Director (CD)

Adverse events, non-compliance both serious or continuing, protocol deviations both major and minor, as well as unanticipated problems are defined and described by the NIH Office of Human Subjects Research Protection policy #801, and will be reported in accordance with this policy.

9.2 Replacement of a Participant Who Discontinues Study Participation

Participants lost to follow-up, drop out, or are unable to participant any longer will be replaced at the discretion of the Principal Investigator.

10 Remuneration Plan for Subjects

The amount of payment to research volunteers is guided by the National Institutes of Health policies. In general, participants are not paid for taking part in research studies at the National Institutes of Health. Meals will be provided to participants.

Participants will be compensated for research-related discomfort and inconveniences in accord with NIH guidelines. Compensation of \$600 or more in one year will be reported to the IRS per federal regulation. The participants will be given 30 dollars at the Screening visit (Visit 0); The maximum amount allowable for the study is 1870 dollars, unless the study physician asks the participant to return to the NIA Clinical Unit for an unplanned visit. Then they will be paid an additional \$20 for each unplanned visit.

The participant will receive the following for completing each of the study visit:

Screening (Visit 0)	30 dollars
Visit 1	540 dollars
Visit 2	600 dollars
Visit 3	700 dollars
Unplanned Visit	20 dollars

The breakdown of payments is as follows:

Frequent blood sampling	140 dollars
Continuous Glucose Monitor	150 dollars
Food Diary (in-patient)	20 dollars (\$10/day)
Intake Diary (out-patient)	65 dollars
MRI	125 dollars
Activity Monitor/completing steps (in-patient)	25 dollars
34-hour urine collection	50 dollars
Study medication (self-dosing)	100 dollars

11 Study Monitoring Structure

11.1 Site Monitoring Plan

No data and safety monitoring board are required for this study. Data and safety will be monitored by the Principal Investigator.

11.2 Safety Monitoring Plan

All protocols at the NIA follow the NIA Data and Safety Monitoring Plan. This includes using the Level of Risk Assessment Monitoring Guidelines that has been established for the NIA following NIH rules and regulations to ensure good clinical practices in the conduct of clinical research. Participants will be informed about new information from this or other studies that may affect their health, welfare, or willingness to stay in this study.

12 Statistical Considerations

This is a pilot study therefore no power calculation can be done.

12.1 Participant Enrollment and Follow-Up

This is a pilot study of volunteers that consent to join the study. Potential participants who express the desire to be enrolled in the study are screened in the NIA Clinical Research Unit. Participants are enrolled once the informed consent is signed by the participant. Participants lost to follow-up, drop out, or are unable to participate any longer will be replaced at the discretion of the Principal Investigator.

13 Ethics/Protection of Human Subjects

Research conducted under this protocol will be conducted in compliance with the protocol, Good Clinical Practices (GCP) and all applicable regulatory requirements.

13.2 Protection of Vulnerable Subjects (Employees)

Protections for employees and staff participating in this study include 1) assuring that the participation or refusal to participate will have no effect, either beneficial or adverse, on the subject's employment or position at the NIH, 2) giving employees and staff who are interested in participating the "NIH Information Sheet on Employee Research Participation" prior to obtaining consent, and 3) assuring that there will be no direct solicitation of employees or staff.

This study collects sensitive information, i.e. collection of blood for HIV, Hepatitis B and C. The PI will train study staff regarding obtaining and handling potentially sensitive and private information about co-workers through staff discussions and written NIA procedures. Information pertaining to these sensitive blood results will be in the participant's NIH medical record. NIA procedures for medical records will apply for the protection of the employee's privacy and confidentiality.

13.3 Informed Consent Process

Informed consent is a process where information is presented to enable persons to voluntarily decide whether or not to participate as a research subject. It is an on-going conversation between the human research subject and the researchers about the essential information about the study, which begins before consent is given and continues until the end of the subject's involvement in the research. Discussions of essential information about the research will include the study's purpose, duration, experimental procedures, alternatives, risks, and benefits, and subjects will have the opportunity to ask questions and have them answered.

Written informed consent will be obtained from the participant prior to any screening visits, study procedures or treatments. The Principal Investigator or other designated qualified protocol investigators (listed on the protocol's face page) will explain the study in language understandable to the subject. Sufficient time and opportunity will be given for discussion of the research as well as to answer any questions they may have, taking care to minimize or eliminate the perception of coercion or undue influence. The participant and the investigator will sign the current IRB-approved informed consent document. A witness will also sign the consent document to attest only to the validity of the signature of the subject, not the validity or quality of the consent. A copy of the consent will be given to the subject for future reference. The signed documents will be placed in the subject's medical record. The consent process will additionally be documented in the medical record.

The rights and welfare of the participants will be protected by emphasizing to them that the quality of their medical care will not be adversely affected if they decline to participate in this study.

Participants that are employees/staff will be consented in the usual manner as noted above. Because this is a pilot protocol, the inclusion of employees or staff is not anticipated to affect the research outcome, therefore if the subject is a co-worker the

subject may be consented by another co-worker and/or subordinate. The study PI will not be involved in the consenting of employees or staff.

We do not plan or anticipate the enrollment of non-English speaking subjects in this pilot study. The NIA at this location does not have sufficient resources (interpreters) to assist with questions the participant may have during the informed consent process. Therefore, a short form consent will not be utilized.

Subjects may withdraw consent at any time throughout the course of the study.

14 Participant Confidentiality

All records will be kept confidential to the extent provided by federal, state and local law. The study monitors and other authorized representatives may inspect all documents and records required to be maintained by the Investigator, including but not limited to, medical records. Samples and data will be stored using codes assigned by the investigators. Records will be kept locked and all computer entry and networking programs will be done with coded numbers only. Clinical information will not be released without written permission of the subject, except as necessary for audit purposes by the IRB or OHSRP.

When results of an NIH research study are reported in medical journals or at scientific meetings, the people who take part are not named or identified. In most cases, the NIH will not release any information about a participant's research involvement without their written permission. However, if they sign a release of information form, for example, for an insurance company, the NIH will give the insurance company information from the participant's medical record. This information might affect (either favorably or unfavorably) the willingness of the insurance company to sell the participant insurance.

The Federal Privacy Act protects the confidentiality of a participants NIH medical record. However, participants should know that the Act allows for the release of some information from their medical record without their permission, for example, if it is required by the Food and Drug Administration (FDA), members of Congress, law enforcement officials, or authorized hospital accreditation organizations.

15 Data Handling and Record Keeping

15.1 Data Management Responsibilities

Electronic records will be kept using secure computer databases. These databases are password protected and maintained on a secure NIA/NIH Intranet with access limited to authorized NIA staff members. All NIA members who have access to these databases have the proper training on patient confidentiality as well as the required Human Subject Protection Training.

15.2 Data Capture Methods

The study will utilize both hard medical record copies/reports as well as electronic data. Our web-based application supports flexible data capture and reporting. The system is hosted at the NIA in Baltimore, MD. It is accessible via the Internet through the NIH firewall, on both Mac and Windows based computers. An Oracle relational database is utilized to capture and secure data entered through the web interface.

The study will be conducted with the protocol, DHHS, FDA, ICH and all applicable institutional, state and local requirements.

15.3 Source documents and Access to Source Data/Documents

Study data will be collected as noted above. The Principal Investigator is responsible for assuring that the data collected is complete, accurate, and recorded in a timely manner.

Appendix C: Inpatient Food Diary

Sodium-glucose CoTransporter 2 (sGLT2) Inhibitor and Endogenous Ketone Production *Participant Inpatient Food Diary*

Study I.D.: _____ Date: _____ Visit # _____

Time of Day	Approximate Amount (Wt. or Vol)	EXAMPLES FOOD DESCRIPTION (One item per line)
0600	8 FLUID OZ.	TROPICANA ORANGE JUICE WITH EXTRA PULP
	8 FLUID OZ.	COFFEE, REGULAR BREWED
	2 CUPS	KELLOGG'S CORN FLAKES CEREAL WITH.....
	1 CUP	SKIM MILK AND...
	1	MEDIUM BANANA
10:00 A.M.	2 OZ.	FAT FREE, UNSALTED PRETZELS, LABEL INCLUDED
	1 TBSP.	REGULAR MUSTARD
12:00 P.M.	1	TURKEY SANDWICH ON....
	2 SLICES	WHITE "WONDER" BREAD
	3 OZ.	SLICED DELI TURKEY, LOW SALT

Sodium-glucose CoTransporter 2 (sGLT2) Inhibitor and Endogenous Ketone Production
Participant Inpatient Food Diary

Study I.D.: _____ Date: _____ Visit # _____

Drinking water is very important. Please check box after drinking 8 ounces of water. Please drink at least (6) 8 ounces.

(1) (2) (3) (4) (5) (6)

DAY 1 – Page 1

Time of Day	Approximate Amount (Wt. or Vol)	FOOD DESCRIPTION (One item per line)

**Sodium-glucose CoTransporter 2 (sGLT2) Inhibitor and Endogenous Ketone
Production**
Participant Inpatient Food Diary

Study I.D.: _____ **Date:** _____ **Visit #** _____

Time of Day	Approximate Amount (Wt. or Vol)	FOOD DESCRIPTION (One item per line)

--	--	--

DAY 1 – Page 2

**Sodium-glucose CoTransporter 2 (sGLT2) Inhibitor and Endogenous Ketone
Production**
Participant Inpatient Food Diary

Study I.D.: _____ Date: _____ Visit # _____

**Drinking water is very important. Please check box after
drinking 8 ounces of water. Please drink at least (6) 8 ounces.**

(1) (2) (3) (4) (5) (6)

Time of Day	Approximate Amount (Wt. or Vol)	FOOD DESCRIPTION (One item per line)

DAY 2 – Page 1

**Sodium-glucose CoTransporter 2 (sGLT2) Inhibitor and Endogenous Ketone
Production**
Participant Inpatient Food Diary

Study I.D.: _____ Date: _____ Visit # _____

Time of Day	Approximate Amount (Wt. or Vol)	FOOD DESCRIPTION (One item per line)

DAY 2 – Page 2

Appendix D: Discharge Instructions Visit 1

- ❖ **Should you experience any problems with your I.V. site, notify the nursing staff. Mild tenderness and some bruising are not unusual.**
- ❖ **The Continuous Glucose Monitor will measure and store your sugar levels for up to 14 days. When you return for Visit 2, we will download the data which will show us how your sugar levels are trending throughout the day and night.**

Appendix E: Intake Diary

sGLT2 Inhibitor – INTAKE DIARY
PLEASE RECORD TIME YOU PUT ANYTHING INTO YOUR MOUTH,
OTHER THAN WATER

Day 1 - Date	Day 2 - Date	Day 3 - Date	Day 4 - Date	Day 5- Date	Day 6- Date	Day 7 - Date	Day 8 - Date	Day 9 - Date
Time hh:mm (am/pm)	Time hh:mm (am/pm)	Time hh:mm (am/pm)	Time hh:mm (am/pm)	Time hh:mm (am/pm)	Time hh:mm (am/pm)	Time hh:mm (am/pm)	Time hh:mm (am/pm)	Time hh:mm (am/pm)

IF YOU RUN OUT OF LINES, PLEASE USE THE BACK OF THIS FORM TO RECORD EATING/DRINKING

sGLT2 Inhibitor- INTAKE DIARY
PLEASE RECORD TIME YOU PUT ANYTHING INTO YOUR MOUTH,
OTHER THAN WATER

Day 10 - Date	Day 11 - Date	Day 12 - Date	Day 13 - Date	Day 14- Date	Day 15- Date	Day 16 - Date
Time hh:mm (am/pm)	Time hh:mm (am/pm)	Time hh:mm (am/pm)	Time hh:mm (am/pm)	Time hh:mm (am/pm)	Time hh:mm (am/pm)	Time hh:mm (am/pm)

IF YOU RUN OUT OF LINES, PLEASE USE THE BACK OF THIS FORM TO RECORD EATING/DRINKING

Appendix F: Discharge Instructions Visit 2

- ❖ Should you experience any problems with your I.V. site, notify the nursing staff. Mild tenderness and some bruising are not unusual.
- ❖ The *Continuous Glucose Monitor* will measure and store your sugar levels for up to 14 days. When you return for Visit 2, we will download the data which will show us how your sugar levels are trending throughout the day and night.

The sensor is comfortable enough to forget it is there. However, use care to avoid catching the sensor on clothing while getting dressed.

Intense exercise may cause the sensor to loosen due to sweat or movement of the sensor. Please contact us if you have any skin irritation or discomfort or if the sensor should become loose or removed.

Your sensor is water resistant and can be worn while bathing, showering or swimming as long as you:

- Do not take it deeper than 3 feet
- Do not keep it under water for longer than 30 minutes at a time.

If necessary, notify security at the airport checkpoint that you are wearing the device. If you have an MRI or CT scan for medical purposes, you must remove your sensor prior to the procedure and notify us.

- ❖ Try to eat the same times each day. Record what times you are eating or drinking on the log provided.
- ❖ Please drink plenty of fluids. Drink at least 8 ounces of water every 4 hours, except when asleep.
- ❖ Please maintain good hygiene to prevent urinary tract or yeast infections. Daily baths/showering recommended.
- ❖ *Study Medication:*

Appendix G: Medication Log

Medication Log (Page 1 of 2)			
*** Remember to take study medication empagliflozin (Jardience) 1 pill every morning, followed by breakfast within 30 minutes			
DRINKING WATER IS VERY IMPORTANT			
Please check box after drinking 8 ounces of water. Please drink at least (6) 8 ounces.			
Day 1 __/__/__ Saturday	Time pill taken	Breakfast time	Comments/Symptoms WATER: 8 OUNCES (1)  (2)  (3)  (4)  (5)  (6) 
Day 2 __/__/__ Sunday	Time pill taken	Breakfast time	Comments/Symptoms WATER: 8 OUNCES (1)  (2)  (3)  (4)  (5)  (6) 
Day 3 __/__/__ Monday	Time pill taken	Breakfast time	Comments/Symptoms WATER: 8 OUNCES (1)  (2)  (3)  (4)  (5)  (6) 
Day 4 __/__/__ Tuesday	Time pill taken	Breakfast time	Comments/Symptoms WATER: 8 OUNCES (1)  (2)  (3)  (4)  (5)  (6) 
Day 5 __/__/__	Time pill taken	Breakfast time	Comments/Symptoms

Wednesday			WATER: 8 OUNCES (1)  (2)  (3)  (4)  (5)  (6) 
Day 6 ___/___/___ Thursday	Time pill taken	Breakfast time	Comments/Symptoms WATER: 8 OUNCES (1)  (2)  (3)  (4)  (5)  (6) 
Day 7 ___/___/___ Friday	Time pill taken	Breakfast time	Comments/Symptoms WATER: 8 OUNCES (1)  (2)  (3)  (4)  (5)  (6) 
Day 8 ___/___/___ Saturday	Time pill taken	Breakfast time	Comments/Symptoms WATER: 8 OUNCES (1)  (2)  (3)  (4)  (5)  (6) 
Medication Log (Page 2 of 2)			
*** Remember to take study medication empagliflozin (Jardience) 1 pill every morning, followed by breakfast within 30 minutes			
DRINKING WATER IS VERY IMPORTANT Please check box after drinking 8 ounces of water. Please drink at least (6) 8 ounces.			
Day 9 ___/___/___ Sunday	Time pill taken	Breakfast time	Comments/Symptoms WATER: 8 OUNCES (1)  (2)  (3)  (4)  (5)  (6) 
Day 10 ___/___/___ Monday	Time pill taken	Breakfast time	Comments/Symptoms WATER: 8 OUNCES (1)  (2)  (3)  (4)  (5)  (6) 
Day 11 ___/___/___ Tuesday	Time pill taken	Breakfast time	Comments/Symptoms WATER: 8 OUNCES (1)  (2)  (3)  (4)  (5)  (6) 
Day 12 ___/___/___ Wednesday	Time pill taken	Breakfast time	Comments/Symptoms WATER: 8 OUNCES (1)  (2)  (3)  (4)  (5)  (6) 
Day 13 ___/___/___ Thursday	Time pill taken	Breakfast time	Comments/Symptoms WATER: 8 OUNCES

			(1)  (2)  (3)  (4)  (5)  (6) 
Day 14 ___/___/___ Friday	Time pill taken	Breakfast time	Comments/Symptoms WATER: 8 OUNCES (1)  (2)  (3)  (4)  (5)  (6) 
Day 15 ___/___/___ Saturday	Time pill taken	Breakfast time	Comments/Symptoms WATER: 8 OUNCES (1)  (2)  (3)  (4)  (5)  (6) 
Day 16 ___/___/___	Time pill taken	Breakfast time	Comments/Symptoms WATER: 8 OUNCES (1)  (2)  (3)  (4)  (5)  (6) 

Appendix H: Discharge Instructions Visit 3

Appendix I: Symptom Review

I.D.# - ____ **Date:** _____ **Time:** _____ **Visit #** _____

Do you have any of the following symptoms?

Symptom	Yes	No	Comment
Dizziness			
Lightheadedness			
Weakness			
Yeast infection (i.e. itching, burning, redness, smelly discharge from genital area)			
Genital infection: tenderness, pain, swelling, flu-like symptoms			
Burning on urination			
Nausea			
Vomiting			
Diarrhea			
Constipation			

Confusion			
Feeling shaky			
Increased hunger			
Decreased hunger			
Headache			
Irritability			
Palpitations			
Anxiety			
Coughing			
Sneezing			
Nasal congestion			
Runny nose			
Fever			
Sore throat			
Shortness of breath			
Other			

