2.2 Secondary Objectives

- To determine the effects of such inhibition on a range of hormones and metabolites: insulin, glucagon, amino and fatty acid levels, especially overnight.
- To determine the effects of such inhibition on plasma exosomes biomarkers related to ketone metabolism (such as MCTs, receptors, intracellular mediators of insulin signaling and ketone metabolism).
- To determine the effects of such inhibition on brain MRS measures of neuronal integrity and metabolism (NAA, glucose, lactate).
- To investigate if this age group will tolerate this class of anti-diabetic drugs, for re-purposing.

3 Study Design

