- l. A staff member will phone participants daily to assure they are taking the study medication and to assess for any symptoms. We will also remind them about the importance to hydrate, as stated above (f).

5.5 Visit 3 occurs 13 +/- 2 days from Visit 2

At Visit 3, the enrolled participant will come to the NIA Clinical Research Unit for a two-day visit, lasting approximately 34 hours. The following procedures will be done:

- a. Height/weight, orthostatic blood pressure measurements, pulse, temperature, respirations and pulse oximetry.
- b. I.V. placement for fasting blood tests (fasting for at least 8 hours) including CMP, lipids, insulin and other hormones. The study drug empagliflozin (Jardiance) will be administered at approximately 8:00 a.m. followed by blood sampling the same as visits 1 and 2. Breakfast will be given within 30 minutes of dosing.
- c. Placement of a continuous glucose monitor (CGM) used to collect data for up to 14 days, worn by the participant until the end of Visit 3.
- d. 34-hour urine collection for creatinine clearance, C-peptide, and other hormones.
- e. All meals will be provided. They will aim to be consistent items and times as what was consumed on Visits 1 and 2. Participants will be also be instructed to hydrate. This includes drinking 8 ounces of water every 4 hours except when asleep.
- f. On the evening of Day 1, the participants will be given an activity monitor and will be instructed to walk 2,000 steps before bedtime.
- g. Day 2: Participants will receive empagliflozin (Jardiance) 25 mg followed by breakfast within 30 minutes.
- h. Brain MRS and limited brain MRI for voxel placement, required anatomical studies and resting functional connectivity will be conducted.

- i. Following the final blood draw, participants will have completed the study. They will no longer take the study medication or wear the CGM.
- j. Discharge instructions will be given (Appendix G).

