5.6 Follow-up Phone Call

Participants will be contacted by a staff member within one week to assess whether they are having any symptoms.

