Empagliflozin (Jardiance) is an FDA approved drug used to treat type 2 diabetes. It is effective in lowering blood glucose levels in type 2 diabetic subjects, however, it is not known to lower blood glucose below normal levels (13). In other words, hypoglycemia is not a side-effect, it has not been reported to occur and is not therefore expected. An oral dose of 25 mg will be administered in the morning of days 1 and 2 of Visit 2. The participants will continue the study medication by self-administering for 13 +/- 2 days at home and recording on the medication log the time that they take their dose (Appendix G). The study medication will be discontinued at the end of Visit 3.

Diet Instructions/Records

Participants will be asked to record what they eat and drink during their inpatient visit on the Food Diary (Appendix C). They will be instructed on the importance of drinking 8 ounces of water every 4 hours, except when asleep. At discharge, they will be instructed to try and eat at the same times each day and record what time they eat or drink anything other than water on the Intake Diary (Appendix E).

Symptom Review Questionnaire

This will be used to assess the participant for any symptoms while taking the study medication. (Appendix I).

Compliance and symptom monitoring

Participants will be contacted daily between Visits 2 and 3 (during the days of self-administration of study drug) to ensure compliance and assess for any symptoms. We will also remind them about the importance of drinking water. It is imperative that participants do not miss 2 consecutive days of study medication or they will be excluded. The goal will be 100 percent compliance, however, greater than 90% will be acceptable.

Brain MRI: In total, structural MRI, fMRI and MRS will last about 1 hour.

- Structural MRI -- Standard structural brain images will be collected for coregistration, MRS voxel placement and to allow for clinical over-read.
- Resting state fMRI study in a single run. Subjects will be asked to keep their eyes open and fixate on a cross. This study will be used to assess intrinsic functional connectivity between different brain regions ⁶.

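### The symptom form asks in the present tense with no recall period, so brief symptoms that have resolved before the contact may be under-counted in the tolerability data

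*Combined protocol and SAP*

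**What the plan says.** Section 2.2 makes tolerability a secondary objective: "To investigate if this age group will tolerate this class of anti-diabetic drugs, for re-purposing".

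The texts on collecting symptoms are these:

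- **Appendix I, Symptom Review.** One date, one time and a visit number at the top, then the stem "Do you have any of the following symptoms" over a list of named symptoms and an Other row. The answer columns are Yes, No and Comment. There is no recall period and no field for start, stop or severity.
- **Section 6.1, on that form.** "This will be used to assess the participant for any symptoms while taking the study medication".
- **Section 6.1, on compliance calls.** Participants are "contacted daily between Visits 2 and 3 (during the days of self-administration of study drug) to ensure compliance and assess for any symptoms". Section 5.4, item l, says much the same: "A staff member will phone participants daily to assure they are taking the study medication and to assess for any symptoms". Neither names Appendix I as the script.
- **Section 5.6.** A single call within one week, "to assess whether they are having any symptoms".
- **Appendix G, Medication Log.** Each home day, 1 to 16, has a free-text field headed "Comments/Symptoms WATER: 8 OUNCES". Section 6.1 describes the log only as a record of dose times.
- **Section 6, procedures table.** Adverse event monitoring is marked in all five columns, including the home-dosing period. The columns end at Visit 3.

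**The concern.** Section 6.1 gives the form a period to cover, namely the time on study drug. The form's stem, read as written, asks about the moment of contact. Several listed symptoms can be short-lived, such as dizziness, lightheadedness, nausea, feeling shaky and palpitations. Section 7.1 names dizziness and lightheadedness among the most common reactions and nausea among the other possible ones. A participant who felt lightheaded in the morning, is well at the call and takes the question at face value could truthfully tick No.

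What is at stake is the completeness of the symptom data behind the tolerability objective. Section 4.1 says safety in this non-diabetic age group needs assessing, and section 7.2 says the pilot's data will be used to design a treatment study. With 20 planned completers, a few missed episodes would visibly change a count. The ketone primary endpoint is not affected.

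**Working it through.** The plan gives no symptom rate, episode length or capture figure, so there is nothing to reproduce. The check has two parts.

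**1. Purpose against wording.** Section 6.1 describes a period; the Appendix I stem describes the present, with no phrase such as *since we last spoke* to widen it. Without start and stop fields, a Yes cannot be dated to a dose, and a resolved episode has no natural place except the Comment column or the Other row. Section 5.6 states the purpose of its call in the present tense, although the call may come days after discharge. No log is visible for that interval, and the procedures table has no column for it.

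**2. How much a literal present-tense question could miss.** This is an illustration, not an estimate. The assumptions are mine: the form is the only source, the answer is literal, there is one contact every 24 hours, and onset is uniform over the interval. The documents supply only the daily frequency and the 13 ± 2 days of home dosing (11 to 15 days).

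For a single episode of length *d* hours, P(present at contact) = min(1, *d*/24). If episodes occur only in a 16-hour waking day, replace 24 by 16 for short *d*.

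| Episode length | 24 h basis | 16 h waking basis |
|---|---|---|
| 1 h | 1/24 = 4.2% | 1/16 = 6.3% |
| 4 h | 4/24 = 16.7% | 4/16 = 25% |
| 12 h | 12/24 = 50% | – |
| 24 h | 24/24 = 100% | – |

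For a symptom that recurs once a day at random times over *n* days, P(at least one Yes) = 1 − (1 − *d*/24)^*n*.

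| Episode length | *n* = 11 | *n* = 15 |
|---|---|---|
| 1 h | 37% | 47% |
| 4 h | 87% | 94% |
| 6 h | 96% | 99% |

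So the exposure is to isolated or very short episodes. A symptom lasting several hours and recurring daily is almost always recorded at least once.

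For the call in section 5.6, read as within a week of Visit 3 and assumed to be made at the end of that week, the interval is 7 × 24 = 168 hours. The same formula gives 1/168 = 0.6% for 1 hour and 4/168 = 2.4% for 4 hours. The gap is widest there, although that call covers days after the drug has been stopped.

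**The case against.** The best case for the plan has four parts.

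*Participants may not answer literally.* Rows such as vomiting, diarrhea and constipation make little sense as a question about one instant, and most people would answer for the recent past. That stands. The wording is ambiguous, and a No for a resolved symptom is possible rather than certain.

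*There are other routes.* A reader might infer that the log is the only other place a passed symptom could appear. The documents do not support that: the form has a Comment column and an Other row, the daily calls are open to any symptom, section 7.1 adds questions on genital symptoms, fever and feeling unwell, and adverse event monitoring is marked throughout. On the unit, blood draws every 1 to 2 hours keep staff close by. These routes would recover some episodes, but the share is unknown and no text we can read ties them together. Parts of the discharge instructions were not available to us, so nothing is inferred from their absence.

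*The form may not be the daily-call script.* This also stands; its header carries a visit number and no text links it to the calls. The 24-hour interval above is therefore an assumption. If the form were completed only at visits, the interval would be longer.

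*No tolerability result is defined.* Correct: the plan names no endpoint, source or summary for that objective. That is a separate gap. It also means one cannot say that events drop out of a specified analysis, only that the data collected may be incomplete.

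**Conclusion.** The point holds as a mismatch between the form's wording and its stated purpose. Brief symptoms that have resolved before the contact may be under-counted, most plausibly at the single call after Visit 3, for which no log is visible. Form alone and with literal answers, capture of one isolated episode is about 4% to 6% for 1 hour and 17% to 25% for 4 hours. Actual loss will be smaller by an unknown amount.

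A reader might go further and infer that the drug will look better tolerated than it is. For example, if 8 of 20 participants each had one 1-hour episode, 8 × 1/16 = 0.5 would be recorded, that is 2.5% instead of 40%. The documents do not support this. They give neither that rate nor that duration, and the result requires every other route to fail; it is a form-alone worst case. This is a cheap improvement to data capture, not a flaw that undermines the trial.

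**What to change.** 1. Change the Appendix I stem to: *Since your last contact (date/time ____), have you had any of the following, even if it has gone away?*
2. Add start, stop and severity columns beside Yes/No/Comment.
3. Word the section 5.6 call the same way, asking about the time since the end of Visit 3.
4. State that at Visit 3 the form is reconciled with the Comments/Symptoms entries in the medication log and with the adverse event record.

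The cost is one reworded form, one sentence in section 5.6 and one added sentence on reconciliation. Calls will be slightly longer and reported symptom counts somewhat higher. No dose, schedule or clinical rule changes.
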